### 1565 **9.3. Primary Analyses**

1566 The primary analysis will follow the intention-to-treat principle. It will include all randomized  
1567 subjects, the data from whom will be analyzed in the group to which the subjects were assigned  
1568 through randomization.

1569  
1570 The intervention will be declared effective only if a statistically significant result (p-value<0.05) is  
1571 obtained for both co-primary outcomes. The type 1 error is therefore not inflated by two co-primary  
1572 outcomes.

#### 1573 **9.3.1. Changes in CGM-Measured % below 70 mg/dL from Run-in to 3-Months Post- 1574 Randomization Period between the Two Treatment Arms**

1575 Summary statistics (median, quartiles) will be reported for the CGM % <70 mg/dL by treatment group.

1576 Changes from run-in pre-randomization CGM wear (data generated as described above) to the 3-month  
1577 post-randomization period in CGM-measured % <70 mg/dL between two treatment arms will be  
1578 compared using a linear mixed effects regression model with a  $\log(x+0.005)$  transformation while  
1579 adjusting for the baseline CGM % <70 mg/dL and clinical center (random effect). Residual values will  
1580 be examined for an approximate normal distribution. If values are highly skewed even after the  
1581 transformation, then an alternate transformation or robust statistical method (e.g., non-parametric or  
1582 MM estimation) will be used instead.

#### 1583 **9.3.2. Changes in CGM-Measured % above 180 mg/dL from Run-in to 3-Months Post- 1584 Randomization Period between the Two Treatment Arms**

1585 Summary statistics (median, quartiles) will be reported for the CGM % >180 mg/dL by treatment  
1586 group.

1587 Changes from run-in pre-randomization to over 3-months post-randomization in CGM-measured %  
1588 >180 mg/dL between two treatment arms will be compared using a linear mixed effects regression  
1589 model; while adjusting for % >180 during run-in, and clinical center (random effect). A 2-sided 95%  
1590 confidence interval for the difference between treatment arms will be generated. Separate two-sided p-  
1591 values will be calculated to test non-inferiority and superiority. Since non-inferiority is often denoted  
1592 in terms of a one-sided test, it is worth noting that a two-sided test at alpha = 0.05 gives the same  
1593 rejection region in the right tail as a one-sided test at alpha = 0.025. It is also worth noting that the  
1594 additional hypothesis test for superiority does not inflate the overall alpha since a type 1 error can only  
1595 occur if the two-sided 95% confidence interval fails to contain the true difference. Residual values will  
1596 be examined for an approximate normal distribution. If values are highly skewed then a  
1597 transformation or robust statistical method (e.g., non-parametric or MM estimation) will be used  
1598 instead.

1599  
1600  
1601  
1602  
1603

1604 **9.4. Secondary Efficacy Analyses**  
1605 In secondary analyses, treatment group differences will be assessed for additional CGM metrics and  
1606 HbA1c. For all secondary analyses (including sections 9.5, 9.6, and 9.7), the false discovery rate will  
1607 be controlled using the adaptive Benjamini-Hochberg procedure with <0.10 as the threshold for  
1608 statistical significance.

1609  
1610 Secondary glycemic metrics based on CGM data will include the following outcomes:  
1611

1612 **CGM Metrics Related to Overall Control**  
1613 - mean glucose  
1614 - % in range of 70-180 mg/dL  
1615 - % in range 70-140 mg/dL  
1616 - glucose variability measured with the coefficient of variation  
1617

1618 **CGM Metrics Related to Hypoglycemia**  
1619 - % <60 mg/dL  
1620 - % <54 mg/dL  
1621 - low blood glucose index  
1622 - hypoglycemia events (defined as at least 15 consecutive minutes <70mg/dL)  
1623

1624 **CGM Metrics Related to Hyperglycemia**  
1625 - % >250 mg/dL  
1626 - % >300 mg/dL  
1627 - high blood glucose index  
1628

1629 The analyses for the above CGM will parallel those mentioned above for the primary % below 70  
1630 mg/dL outcome, with the exception that a transformation will not be used for those metrics with a  
1631 distribution that is approximately normally distributed. Summary statistics will be reported mean  $\pm$  SD  
1632 or median (quartiles) as appropriate to the distribution.  
1633

1634 A comparison of primary and secondary results during the daytime and overnight will be made.  
1635

1636 **HbA1c**  
1637 Change in HbA1c from baseline to 13 weeks will be compared between the two treatment arms using a  
1638 linear model while adjusting for baseline HbA1c and clinical center (random factor).  
1639

1640 Several binary outcomes will be compared between treatment groups using central lab HbA1c values.  
1641 • HbA1c <7.0% at 13 weeks  
1642 • HbA1c <7.5% at 13 weeks  
1643 • HbA1c improvement from baseline to 13 weeks  $\geq$ 0.5%  
1644 • HbA1c improvement from baseline to 13 weeks  $\geq$ 1.0%  
1645 • HbA1c relative improvement from baseline to 13 weeks  $\geq$ 10%  
1646 • HbA1c improvement from baseline to 13 weeks  $\geq$ 1.0% or HbA1c <7.0% at 13 weeks  
1647

1648 Our goal is to minimize the amount of missing data and it is worth noting that all statistical methods  
1649 for handling missing data rely on untestable assumptions and there is no one correct way to handle  
1650 missing data. If some HbA1c data will be missing, in addition to the completer-only analyses

1651 mentioned above, sensitivity analyses will be performed in order to confirm that the conclusions do not  
1652 rely on the statistical methods employed for handling missing data. Replication of the HbA1c analyses  
1653 with imputed data for subjects with missing both local and central lab HbA1c at 13 weeks will be done  
1654 using two methods:

- Rubin's multiple imputation and
- Direct likelihood

1657

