400 Investigational device components may be used by study staff for the purpose of system training and  
401 troubleshooting as long as there is no insulin infusion.

402                   **CHAPTER 2: SUBJECT SCREENING AND ENROLLMENT**

403

404                   **2.1. Study Population**

405 Enrollment will proceed with the goal of randomizing 126 subjects and having at least 110  
406 subjects with sufficient data to include in the primary analysis. A maximum of 200 subjects may  
407 be enrolled in the study in order to achieve the goal of randomizing 126 subjects.

408

409 In order to have a broad range of glycemic control among the subjects, a study goal will be to  
410 have a minimum of 50 subjects with HbA1c  $\geq 7.5\%$  and 50 with HbA1c  $< 7.5\%$ .

411

412                   **2.2. Eligibility and Exclusion Criteria**

413

414                   **2.2.1. Eligibility**

415 To be eligible for the study, a subject must meet the following criteria:

- 416     1) Clinical diagnosis, based on investigator assessment, of type 1 diabetes for at least one year  
417        and using insulin for at least 1 year
- 418     2) Use of an insulin pump for at least 6 months
- 419     3) Age  $\geq 14$  years old
- 420     4) HbA1c level  $< 10.5\%$  at screening
- 421     5) For females, not currently known to be pregnant
  - 422        • *If female and sexually active, must agree to use a form of contraception to prevent  
423            pregnancy while a participant in the study. A negative serum or urine pregnancy test  
424            will be required for all females of child-bearing potential. Subjects who become  
425            pregnant will be discontinued from the study. Also, subjects who during the study  
426            develop and express the intention to become pregnant within the timespan of the  
427            study will be discontinued.*
- 428     6) Willingness not to add non-insulin glucose-lowering agents (such as Pramlintide, Metformin,  
429        GLP-1 analogs, SGLT2 inhibitors) during the study
- 430     7) Willingness, if not assigned to the closed-loop group, to avoid use of any closed-loop control  
431        system for the duration of the clinical trial
- 432     8) Willingness to suspend use of any personal CGM for the duration of the clinical trial  
433        beginning with the unblinded study CGM run-in period

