## CHAPTER 4: Randomized Trial

662  
663 **4.1. Randomization Visit**  
664  
665 **4.1.1. Timing of Visit**  
666 The randomization visit may occur concurrently with the Enrollment Visit for subjects who meet CGM  
667 use requirements described above. Otherwise, the visit will be concurrent with the Unblinded CGM  
668 Run-in Review Visit.  
669  
670 Subjects will receive supplies for blood glucose and ketone testing and associated use guidelines and a  
671 prescription for a glucagon emergency kit if needed, as described above. Subjects will be advised to  
672 contact the manufacturer's technical support center for technical issues with the study CGM and to call  
673 the study physician for any health related issues.  
674  
675 A urine pregnancy test will be repeated for all females of child-bearing potential who participated in  
676 the CGM run-in phase.  
677  
678 **4.1.2. HbA1c**  
679 HbA1c will be measured using DCA Vantage or similar POC device or local lab. A blood sample will  
680 also be drawn to send to the central laboratory for baseline HbA1c determination to be used in outcome  
681 analyses.  
682  
683 **4.1.3. Baseline C-Peptide Assessment**  
684 A blood sample will be drawn to send to the central laboratory for a random, non-fasting C-peptide  
685 determination to characterize baseline residual insulin production.  
686  
687 **4.1.4. Randomization**  
688 Eligible subjects will be randomly assigned to one of two treatment groups in a 1:1 ratio:  
689 1. Control-to-Range (CTR) Closed-Loop Group  
690 2. SAP Group  
691  
692 The subject's randomization group assignment is determined by completing a Randomization Visit case  
693 report form on the study website. The randomization list will use a permuted block design, stratified by  
694 clinical center.  
695  
696 *The subject will be included in the data analysis regardless of whether or not the protocol for the  
697 assigned randomization group is followed. Thus, the investigator must not randomize a subject until  
698 he/she is convinced that the subject/parent will accept assignment to either of the two groups.*  
699  
700 **4.1.5. Questionnaires**  
701 Subjects will complete a set of baseline questionnaires, described in section 5.1, prior to  
702 randomization. Subjects randomized into the CTR group will also complete an additional Technology  
703 Expectation Survey after randomization.  
704  
705 **4.2. Procedures for the CTR Group**  
706  

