## CHAPTER 9: STATISTICAL CONSIDERATIONS

1511  
1512  
1513 The approaches to sample size and statistical analyses are summarized below. A detailed statistical  
1514 analysis plan will be written and finalized prior to the completion of the study.  
1515  
1516 The co-primary outcomes for this study are CGM-measured % below 70 mg/dL and % above 180  
1517 mg/dL over a 3-month period. The intervention will be considered effective if both of the following  
1518 comparisons between two treatment arms (SAP vs. CTR) are statistically significant ( $p < 0.05$ ):  
1519

- superiority test for % time CGM values below 70 mg/dL and
- non-inferiority test for % time CGM values above 180 mg/dL (non-inferiority limit = 5%).

  
1520  
1521  
1522 **9.1. Sample Size**  
1523 Sample size has been computed using co-primary outcomes of time  $<70$  mg/dL (superiority) and time  
1524  $>180$  mg/dL (non-inferiority). Data from the CGM arm of the JDRF CGM RCT from subjects meeting  
1525 the eligibility criteria for the current trial were used to project the distribution of % below 70 and above  
1526 180 mg/dL over 3 months as measured by CGM for the SAP group in the proposed study.  
1527  
1528 The total sample size was computed to be 110 for the following assumptions: (1) 1:1 randomization,  
1529 (2) 90% power, with adjustment to account for the two co-primary analyses, (3) a 50% relative  
1530 reduction in time  $<70$  mg/dL (or absolute reduction of 2.0% assuming baseline of 4.0%) with an  
1531 effective SD of 2.8% and 2-sided type 1 error of 5%, and (4) a non-inferiority limit of 5% for the  
1532 treatment group comparison of time  $>180$  mg/dL and assuming there is a true difference of 2.5%  
1533 favoring the CTR group, with an effective standard deviation of 11% and a 1-sided type 1 error of  
1534 2.5%. The sample size was increased to 126 to account for subjects with insufficient data to include in  
1535 the primary analysis (see section 9.2).  
1536  
1537 The Appendix provides further details of the sample size assumptions and computations.  
1538  
1539 **9.2. Calculation of Outcome Metrics and Handling of Missing Data**  
1540 *CGM Metrics*  
1541 Randomization is preceded by two weeks of blinded CGM run-in or by presenting at least three weeks  
1542 of personal CGM data. The two weeks of blinded run-in or the last two weeks of personal CGM data  
1543 will be used in the calculation of baseline CGM metrics.  
1544  

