1545 Per protocol design, the first two weeks following the randomization visit involve a training schedule  
1546 for both groups. CGM data during this time will not be included in the calculation of the outcome  
1547 CGM metrics. Unblinded CGM data starting from Week 3 post-randomization through the 3 month  
1548 visit will be included in the calculation of each CGM metric. Missing (or less than 168 hours) post-  
1549 randomization unblinded sensor data will be imputed using all available post-randomization blinded  
1550 data. Subjects with any amount of post-randomization unblinded or blinded data will be included in  
1551 CGM analyses. Percentages  $<70$  and  $>180$  mg/dL will be calculated giving equal weight to each CGM  
1552 point for each subject.  
1553  
1554 The two weeks of blinded CGM data collected after 9 weeks will not be used for the primary outcome;  
1555 except for imputations as mentioned above.  
1556  
1557 *HbA1c*

1558 If the 3-month visit is completed but an HbA1c measurement from the central laboratory is not  
1559 available, a local HbA1c measurement made at the clinical site at the 3-month visit will be used if  
1560 available. In such cases the HbA1c value used in the analysis will be computed from a regression line  
1561 using the available lab-local HbA1c pairs. A similar imputation will be done for any missing lab  
1562 HbA1c values at baseline or other visits. If neither measurement at 3 months is available, then the  
1563 HbA1c value will be considered missing and the subject will be excluded from all HbA1c analyses.  
1564

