## 1693 **9.7. Subgroup Analyses**

1694 In exploratory analyses, the two primary outcomes (%  $<70$  and  $>180$  mg/dL) will be assessed  
1695 separately in various subgroups and for continuous variables according to the baseline value as defined  
1696 below. Tests for interaction with treatment group will be performed and further explored if an  
1697 interaction will be found in the first place.

1698  
1699 Interpretation of subgroup analyses will depend on whether the overall analysis demonstrates a  
1700 significant treatment group difference. In the absence of such an overall difference and if performed,  
1701 subgroup analyses will be interpreted with caution. For continuous variables, results will be displayed  
1702 in subgroups based on cutpoints although the analysis will utilize the variable as continuous, except for  
1703 age which will be analyzed both as a continuous variable and in two age groups. If there is insufficient  
1704 sample size in a given subgroup, the cutpoints for continuous measures may be adjusted per the  
1705 observed distribution of values. Cutpoint selection for display purposes will be made masked to the  
1706 outcome data.

- 1707 - Baseline HbA1c (as continuous variable and in the two subgroups  $\geq 7.5\%$  and  $< 7.5\%$ )
- 1708 - Baseline CGM time spent  $< 70$  mg/dL
- 1709 - Baseline CGM time spent  $> 180$  mg/dL
- 1710 - Age: As a continuous variable and in these subgroups
  - 1711     ○  $< 25$
  - 1712     ○  $\geq 25$
- 1713 - Gender
  - 1714     ○ Female
  - 1715     ○ Male
- 1716 - Race
  - 1717     ○ White
  - 1718     ○ Non-White (split if sample size allows)
- 1719 - Clinical site

1720  
1721 Additional analyses may be performed for subgroups defined based on the following baseline  
1722 demographic/clinical characteristics.

- 1723 - body mass index,
- 1724 - income, education, and/or insurance status,
- 1725 - baseline scores for quality of life, hypoglycemia awareness and fear questionnaires
- 1726 - C-peptide level

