### CGM time below 70 mg/dl

Among all 125 subjects in the JDRF data, the mean % below 70 mg/dl over 13 weeks = 4.0%, the mean % below 70 mg/dl during the 2 weeks run-in phase = 3.7%, and the correlation between the two = 0.74. The SD for % below 70 mg/dl over 13 weeks = 3.3% (95% CI: 2.9%, 3.8%). A more conservative correlation of 0.5 was used for an effective SD = 2.8% (95% CI: 2.5%, 3.3%).

1880  
1881 CGM time above 180 mg/dl  
1882 Among all 125 subjects in the JDRF data, the mean % above 180 mg/dl over 13 weeks = 27%, the  
1883 mean % above 180 mg/dl during the 2 weeks run-in phase = 27%, and the correlation between the two  
1884 = 0.80. The SD for % above 180 mg/dl over 13 weeks = 13% (95% CI: 11%, 15%). A more  
1885 conservative correlation of 0.5 was used for an effective SD = 11% (95% CI: 10%, 13%).  
1886  
1887 Combined inference  
1888 For the primary analysis, the intervention will be considered effective only if both co-primary  
1889 outcomes are found to be statistically significant. Instead of inflating the type 1 error, requiring both  
1890 comparisons to be statistically significant slightly inflates type 2 error. The lower bound for the overall  
1891 combined power to reject both null hypothesis will be computed using Bonferroni adjustments.  
1892  
1893 The total sample size was computed to be 110 for the following assumptions:  
1894     - 1:1 randomization scheme,  
1895     - 90% overall power that accounts for the two co-primary analyses,  
1896     - A 50% relative reduction in time <70 mg/dL of (i.e., 4.0% vs. 2.0% absolute time) with an  
1897         effective SD of 2.8% and 2-sided type I error of 5%,  
1898     - A non-inferiority limit of 5% for the treatment group comparison of time >180 mg/dL and  
1899         assuming there is a true difference of 2.5% favoring the CTR group, with an effective standard  
1900         deviation of 11% and a 1-sided type I error of 2.5%.  
1901  
1902 The assumptions above with a sample size of N=110 give statistical power:  
1903     - 96% for the hypoglycemia comparison (superiority) and  
1904     - 94% power for the hyperglycemia comparison (non-inferiority).  
1905  
1906 Using a Bonferroni bound, the overall power that both tests will reject the null hypothesis is at least  
1907 94% + 96% - 100% = 90%.  
1908  
1909 **4. Summary**  
1910 For the primary analysis, the intervention will be considered effective if a statistically significant  

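### Optional gain in precision: the non-inferiority model for % >180 could also adjust for the baseline central-laboratory HbA1c that the trial already measures

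*Combined protocol and SAP*

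**What the plan says.** Section 9.3.2 specifies a linear mixed model for % >180, "while adjusting for % >180 during run-in, and clinical center (random effect". The baseline CGM value covers two weeks and has two possible sources (9.2): "The two weeks of blinded run-in or the last two weeks of personal CGM data".

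On HbA1c, the protocol says the following.

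- Section 4.1.2: at the randomization visit a blood sample will "also be drawn to send to the central laboratory for baseline HbA1c determination to be used in outcome" analyses.
- Section 9.2: a central value missing at 3 months is predicted from the local one by regression, and for baseline "A similar imputation will be done for any missing lab" HbA1c values.
- Section 2.1: "In order to have a broad range of glycemic control among the subjects, a study goal will be to" enroll at least 50 subjects at or above 7.5% and at least 50 below it.
- Section 4.1.4: "The randomization list will use a permuted block design, stratified by" clinical center. No other stratum is named.
- Section 9.7: "Baseline HbA1c (as continuous variable and in the two subgroups" split at 7.5%) is a factor in the exploratory subgroup analyses of the primary outcomes.
- Section 9.4 adjusts the HbA1c outcome for baseline HbA1c. Section 9.11 has no HbA1c-adjusted sensitivity analysis for the primary outcomes.

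Chapter 9 opens by saying that a detailed statistical analysis plan is still to be finalized.

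**The concern.** Non-inferiority on % >180 is judged by whether a 95% confidence interval excludes a 5-point margin, so the residual SD matters directly. Success requires both co-primary outcomes, so an interval that is too wide on % >180 could by itself deny the trial a positive result.

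The enrollment goal is meant to broaden HbA1c, a variable plausibly tied to hyperglycemia. Randomization does not balance it within center, nearly every subject will have a value, and the model leaves it out. The covariate that is used covers only two weeks. For run-in subjects those two weeks come before pump-setting optimization and before two weeks of unblinded CGM; other subjects contribute personal CGM downloads. HbA1c reflects a longer period and is measured in the same way for everyone. It might therefore explain outcome variance that the two-week value misses, and adjusting for it would absorb chance imbalance between arms. In a linear model the treatment effect being estimated would not change.

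**Working it through.** **Inputs (section 9.1 and Appendix).** 55 evaluable subjects per arm (110 in total); margin 5 points; assumed true difference 2.5 points favoring CTR, so 7.5 points from the margin; one-sided alpha 2.5%. The SD of % >180 over 13 weeks is 13%. For the reference data the Appendix gives "mean % above 180 mg/dl during the 2 weeks run-in phase = 27%, and the correlation between the two" as 0.80, but plans on 0.5.

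**Effective SD = 13 × √(1 − r²).**
- r = 0.5: 13 × √0.75 = 11.3, which the plan states as 11.
- r = 0.80: 13 × √0.36 = 7.8.

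**The plan's power, from the non-central t with 108 df.**
- % >180: 7.5 / (11 × √(2/55)) = 7.5 / 2.098 = 3.58, power 94.3% (stated 94%).
- % <70: 2.0 / (2.8 × √(2/55)) = 3.75, power 96.0% (stated 96%).

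Both reproduce. At SD 7.8 the % >180 power is 99.9%. If the true difference is zero (distance 5), power is 66% at SD 11 and 91.5% at SD 7.8.

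**Effect of adding HbA1c.** Let b be its correlation with baseline % >180 and y its correlation with the outcome. The partial correlation is p = (y − b·r) / √((1 − b²)(1 − r²)), and residual variance is multiplied by 1 − p². The documents give neither b nor y; the range 0.4 to 0.7 is assumed. For example, with r = 0.80 and b = y = 0.7, p = (0.70 − 0.56) / √(0.51 × 0.36) = 0.327 and 1 − p² = 0.893.

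| r (starting SD) | b, y | p | Variance falls | SD | Power, planned difference | Power, zero difference |
|---|---|---|---|---|---|---|
| 0.80 (7.8) | no HbA1c | – | – | 7.80 | 99.9% | 91.5% |
| 0.80 | 0.7, 0.56 | 0 | 0% | 7.80 | 99.9% | 91.5% |
| 0.80 | 0.6, 0.5 | 0.042 | 0.2% | 7.79 | 99.9% | 91.5% |
| 0.80 | 0.4, 0.4 | 0.145 | 2% | 7.72 | 99.9% | 92.0% |
| 0.80 | 0.7, 0.7 | 0.327 | 11% | 7.37 | above 99.9% | 94.1% |
| 0.5 (11) | no HbA1c | – | – | 11.0 | 94.3% | 66% |
| 0.5 | 0.7, 0.4 | 0.081 | 0.7% | 10.96 | 94.5% | 66% |
| 0.5 | 0.4, 0.4 | 0.252 | 6% | 10.65 | 95.6% | 68% |
| 0.5 | 0.5, 0.5 | 0.333 | 11% | 10.37 | 96.4% | 71% |
| 0.5 | 0.7, 0.7 | 0.566 | 32% | 9.07 | 99.0% | 82% |

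The rows illustrate assumed pairs and are not bounds. The one degree of freedom that HbA1c costs, out of more than 100, is ignored.

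**The case against.** The strongest reply is that this is a preference. The plan adjusts each CGM outcome for its own baseline and for center, consistently across 9.3 and 9.4. Nothing is contradictory or invalid, and the same remark could be made of any prognostic variable left out. That stands: this is an optional improvement.

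The second reply concerns size. The only correlation observed in the documents is 0.80, and there the planned-difference power has almost no room to rise. The 0.5 was chosen to be conservative. The largest gains pair that pessimistic baseline with an HbA1c that correlates 0.7 with the outcome, so that HbA1c would predict CGM % >180 better than CGM % >180 itself. Nothing in the documents supports that. Equal correlations are also only a convenience; without them the gain can be zero. All of this stands, and it is why zero belongs in the range.

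Third, a wider spread of HbA1c probably also widens the spread of run-in % >180, which is already in the model. That is fair, so the enrollment goal alone does not show a loss.

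What the replies do not show is a disadvantage in adding the covariate, or that it would be useless. The 0.80 comes from the first two weeks of CGM data in the CGM arm of an earlier trial. It may not carry over to a baseline that mixes blinded run-in with personal CGM downloads.

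**Conclusion.** The point holds as an optional, nearly free improvement. On the observed correlation of 0.80 the gain runs from nil to an 11% fall in residual variance in the cases examined: power at the planned difference stays at about 99.9%, and zero-difference power moves from 91.5% to at most 94%. On the planning correlation of 0.5, the fall is about 1% to 32%, power goes from 94.3% to 94.5%–99.0%, and zero-difference power from 66% to 66%–82%. If HbA1c is held to be no better a predictor than the baseline itself (0.5 for both correlations), those figures are 11%, 96.4% and 71%. All of this rests on assumed HbA1c correlations.

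A reader might infer three stronger things that the documents do not support:

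- That the test is underpowered. The stated 94% reproduces without HbA1c, on an SD that is already conservative.
- That not stratifying on HbA1c biases the comparison. Randomization protects against that; only chance imbalance remains, and run-in % >180 may already absorb part of it.
- That a known amount of precision is being lost. The amount cannot be derived from the documents and may be nil.

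**What to change.** In the detailed statistical analysis plan, and in 9.3.2 if it is amended, add 'and baseline central-laboratory HbA1c (continuous)' to the fixed covariates of the % >180 model. Fill a missing baseline central value with the local-to-central regression already set out in 9.2. Keep baseline % >180 and the random center effect. Settle this before any outcome data by arm are seen, because a covariate added later would look data-driven.

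The cost is one phrase and one degree of freedom. No new data, visits or subjects are needed, and the sample size need not change.

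### For HbA1c change, both planned missing-data checks assume missing at random and, without auxiliary data, will essentially repeat the completer analysis; neither tests informative dropout

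*Combined protocol and SAP*

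**What the plan says.** Section 9.4 (HbA1c) sets the main comparison: "Change in HbA1c from baseline to 13 weeks will be compared between the two treatment arms using a" "linear model while adjusting for baseline HbA1c and clinical center (random factor". It is a completer analysis. Under Section 9.2, when neither a central nor a local 3-month result exists, the "HbA1c value will be considered missing and the subject will be excluded from all HbA1c analyses".

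If values are missing, Section 9.4 adds checks to the completer analyses: "mentioned above, sensitivity analyses will be performed in order to confirm that the conclusions do not" "rely on the statistical methods employed for handling missing data. Replication of the HbA1c analyses" "with imputed data for subjects with missing both local and central lab HbA1c at 13 weeks will be done". The two methods are "Rubin's multiple imputation and" "Direct likelihood". The section does not give the imputation variables or the direct-likelihood model, and it names no analysis that departs from missing at random. It does concede that every missing-data method rests on assumptions that cannot be tested.

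Table 3 and Section 4.4.1.1 place the only post-randomization HbA1c measurements, central and local, at the 13-week visit. Section 9.2 mentions other visits, but none with an HbA1c is scheduled between randomization and week 13. Chapter 9 opens by calling itself a summary and defers detail to a later SAP.

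**The concern.** A sensitivity analysis is informative when it changes the assumption under question. Here the assumption is that, given arm, baseline HbA1c and center, people with no 13-week value would have had results like those of people who were measured. With one follow-up value, and the predictors already in the completer model, a subject without that value tells us almost nothing more about the treatment effect. Imputing from the same predictors, or writing down the joint likelihood, keeps both the assumption and the estimate.

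Informative missingness is plausible in this trial. The arms are visibly different, and CTR subjects give up their own pump (Section 1.4.6). The pilot in Section 1.2 reports that HbA1c improvement correlated with system use (r = 0.59). If low users are the ones who leave, the missing CTR values may be worse than the model predicts. Three agreeing analyses could then be read as robustness although this threat was not examined.

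**Working it through.** **Inputs.** The documents give no HbA1c missing rate and no HbA1c power calculation, so there is no plan figure to reproduce.
- HbA1c SD 0.6: Section 1.2, Table 1.
- 126 randomized, 110 evaluable: Section 2.1, giving (126 − 110)/126 = 12.7%. This is the allowance for insufficient data in the CGM primary analysis, borrowed here as an upper illustration; 5% is assumed as a lower one.
- Also assumed: baseline-to-13-week correlation 0.7; true effect −0.2 points (the size of the pilot's before-after change, 7.2 to 7.0); correlation of 0.5 to 0.8 between a CGM-type auxiliary variable and the HbA1c residual.

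**Step 1, direct likelihood.** Write y for 13-week HbA1c and b for baseline. The likelihood factors as f(y | b, arm) × f(b). A subject without y contributes only f(b), which does not contain the treatment effect. Fitting the joint normal model (common baseline mean, no center term) to 200 datasets gave a largest difference from the completer ANCOVA of 1.4 × 10⁻⁸. A version with separate baseline means per arm, contrasting raw change, differed by 0.025 on average. That difference comes from the baseline adjustment, not from the missing-data assumption.

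**Step 2, multiple imputation with the same covariates.** N = 126, 7 centers.
- Centers as fixed effects: mean absolute difference from completers 0.0014 (5% missing) to 0.0026 (12.7%), maximum 0.010; standard error about 0.08.
- Center as a random effect, as planned: the average difference was within 0.001 and the mean absolute difference 0.003 to 0.006, which is imputation noise.

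**Step 3, informative dropout.** CTR subjects with worse HbA1c are made likelier to be missing (center random):

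| Missing | Full data | Completers | Multiple imputation |
|---|---|---|---|
| 5% | −0.201 | −0.220 | −0.220 |
| 12.7% | −0.199 | −0.249 | −0.248 |

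The size of the bias depends on the assumed strength of the mechanism. The agreement between the last two columns does not.

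**Step 4, with an auxiliary variable.** Under outcome-dependent dropout at 12.7% (centers fixed), full data gave −0.192 and completers about −0.27. Imputation using a CGM-type variable gave −0.256 (correlation 0.5) or −0.222 (correlation 0.8). It removes part of the bias and no longer copies the completer result.

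**Step 5, binary outcomes.** For HbA1c below 7.0%, imputing the continuous value and then dichotomizing differed from an unadjusted completer comparison by 1.4 to 2.2 percentage points on average (maximum 7.5). The imputation still assumes missing at random.

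**Step 6, departing from missing at random.** Adding δ to imputed CTR values only shifts the treatment difference by about (CTR missing fraction) × δ:

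| CTR missing | δ = 0.2 | δ = 0.5 | δ = 1.0 |
|---|---|---|---|
| 5% | 0.010 | 0.025 | 0.050 |
| 12.7% | 0.025 | 0.064 | 0.127 |

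To illustrate a tipping point, take an estimate of −0.20 with standard error 0.08. The upper 95% limit is −0.20 + 1.96 × 0.08 = −0.043. Moving it to zero needs δ = 0.043/0.127 = 0.34 at 12.7% missing, but 0.043/0.05 = 0.86 at 5%. A grid that stopped at 0.5 would miss the second. The 1.96 is for illustration only, since Section 9.4 controls the false discovery rate.

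**The case against.** A reader might infer that the two checks duplicate the completer analysis by construction and will always agree with it. The documents do not support that. The imputation model is unspecified and detail is deferred to the SAP. If post-randomization CGM data were included, imputation would differ from completers (Step 4). The analyses to be replicated also include six binary outcomes, which need not be reproduced (Step 5).

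A reader might also infer that the plan claims robustness to informative dropout. It does not: its stated aim is robustness to the statistical method, and the same paragraph admits untestable assumptions.

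Materiality is limited too. HbA1c is secondary, and success rests on the two CGM co-primaries. A calibrated local HbA1c is substituted first (Section 9.2), and subjects who stop treatment stay in follow-up with priority on the 13-week visit (Section 7.9.1). The fully missing fraction may be small.

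Most of this stands and sets the priority. Two parts do not answer the point. The local substitute needs a completed 3-month visit, so it rescues lost central results but not people who miss that visit. And admitting an untestable assumption is different from varying it: neither named method does so, whatever detail the SAP later adds about them.

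**Conclusion.** The point holds for the continuous HbA1c change. With one post-randomization HbA1c, and baseline and center already in the completer model, both named methods share its missing-at-random assumption. Without auxiliary data they return essentially its estimate, within 0.001 to 0.006 points on average under the assumed SD and correlation. Agreement would not be evidence of robustness to informative dropout. The binary checks may differ numerically but also assume missing at random.

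It does not follow that the HbA1c result will be biased toward CTR. The documents give neither an HbA1c missing rate nor a dropout mechanism, so the shifts of 0.025 (5% missing) and 0.064 (12.7%) at δ = 0.5 are illustrations. This is a cheap improvement to a secondary outcome, of low to moderate priority.

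**What to change.** In the SAP:

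1. State the multiple imputation model and include each subject's available post-randomization CGM mean glucose, which the trial already collects.
2. Add a delta-adjusted (tipping-point) multiple imputation that worsens imputed CTR HbA1c in steps until the conclusion changes. Report that δ and do not stop at a preset ceiling such as 0.5.
3. Keep direct likelihood if wanted, but do not present its agreement with the completer analysis as evidence of robustness.

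The cost is a short SAP paragraph and modest programming. No new data or visits are needed. The auxiliary variable cannot help subjects with no post-randomization CGM, and the imputation that uses it still assumes missing at random, so item 2 is needed as well.
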